### 5.3.2 SSARs

Any SAE that is considered, with a reasonable probability, to be due to study treatment is potentially a SSAR. In making this assessment there should be consideration, based on:

- the available information,
- the probability of an alternative cause
- the timing of the reaction with respect to study treatment
- the response to withdrawal of the study treatment
- the response to subsequent re-challenge (where appropriate)

Any potential SSAR which comes to the attention of LCC staff must be reported to the CCO immediately (at least within 24 hours) of becoming aware of it. The following standard information will be obtained and recorded:

- Participant study number
- Identity of reporting person
- Event description
- Reason for attribution to study treatment

All such SSAR reports will be reviewed urgently by the Chief Investigator (or delegated deputy) at the CCO, who will assess the evidence for seriousness and relatedness, seek any additional information required (including relevant information relating to medical history and treatment both prior to and following randomisation), and assess expectedness based on the SmPC.

Any SSAR that is considered to be "unexpected" (i.e. a Suspected Unexpected Serious Adverse Reaction [SUSAR]) will lead to the relevant participant being unblinded. All SUSARs for participants randomized to active fenofibrate will be reported by the CCO to the MHRA and REC in an expedited fashion. For SUSARs that are fatal or life-threatening, an initial report will be submitted within 7 days (*7 day report*) of the date received, with a follow-up report provided within 8 days of the initial report, if required. For all other SUSARs, a 15 day report will be required. The following minimum information will be required for any SUSAR report:

- EudraCT number for the trial (2016-002656-24)
- Name of the suspected study medication (fenofibrate)
- Participant study number
- Identity of reporting person

---

 As recommended by regulatory authorities, a Suspected Serious Adverse reaction (SSAR) should be considered an unanticipated problem requiring expedited reporting only if it is either an event that is uncommon and strongly associated with drug exposure (such as angioedema, agranulocytosis, hepatic injury, or Stevens-Johnson syndrome), or an event that is not commonly associated with drug exposure, but uncommon in the study population (e.g. tendon rupture, progressive multifocal leukoencephalopathy).

- Event description
- Reason for attribution to study treatment
- Treatment assignment after unblinding

Confirmed reports of SSARs and SUSARs will be promptly forwarded to the chairman of the Data Monitoring Committee (DMC) and will be included in the Development Safety Update Report (DSUR) sent to the REC and MHRA. Study treatment will be discontinued in the event of a confirmed SSAR or SUSAR. Local PIs will be informed of any SUSARs which occur during LENS.

#### **5.3.3 Reporting urgent safety measures**

If the Protocol needs to be amended urgently because of a safety concern the CI/Sponsor will immediately, and in any event no later than 3 days from the date the measures are taken, give notice to the MHRA (initially by telephone followed by written notification) and the relevant REC of the measures taken and the circumstances giving rise to those measures.

#### **5.3.4 The type and duration of the follow-up of subjects after AEs**

Any participant experiencing a SSAR or SUSAR will be followed up for the remainder of the trial period and until the event has resolved (whichever is the longer).

#### **5.3.5 Development Safety Update Reports**

The CCO will submit DSURs once a year throughout the clinical trial or, on request, to the MHRA, the REC and the Sponsor.

### **5.4 NOTIFICATION OF SPECIFIC EVENTS**

#### **5.4.1 Deaths**

If a death is reported by LCC staff or via the Freephone service, as much information as possible will be collected, a provisional cause of death assigned and it will be entered into the study database. SSARs or SUSARs will be reported as detailed in section 5.3.2.

#### **5.4.2 Pregnancy**

If a trial participant becomes pregnant, she will be required to discontinue study drug and information regarding her participation in LENS (including study treatment allocation) will be provided to her caring obstetrician. The outcome of the pregnancy will be followed up by the LCC. Information regarding pregnancy will not be collected for male participants whose partners fall pregnant during the trial.

#### **5.4.3 Overdose**

Any overdose of study medication (as defined in Table 5) should be reported to the CCO and sponsor according to the same timelines as SSAR notification. The participant will be required to discontinue study drug but will continue to be followed up in the trial.

## 5.5 RESPONSIBILITIES

### 5.5.1 LCC PI and LCC research nurse:

- Ensuring that details of SAEs and NSAEs that lead to the cessation of study treatment that are reported to the LCC are recorded in the TMS
- Ensuring that all SSARs (including any suspected SUSARs) that are reported to the LCC are recorded and reported to the CCO within 24 hours of becoming aware of the event and provide further follow-up information as soon as available.

### 5.5.2 Chief Investigator (CI):

- Clinical oversight of the safety of patients participating in the trial, including an ongoing review of the risk / benefit.
- Assessment of seriousness, relatedness and expectedness of potential SSARs and SUSARs.
- Immediate review of all SUSARs (this role will be fulfilled by a nominated deputy when the CI is unavailable).
- Review of SSARs in accordance with the trial risk assessment and protocol
- Assigning Medical Dictionary for Regulatory Activities (MedDRA) coding to all SAEs and SSARs.
- Preparing the clinical sections, reviewing the SmPC for any updates and final sign off of the DSUR.
- Unblinding of a participant for the purpose of expedited SUSAR reporting.

[Note: these responsibilities may be delegated to one or more suitably qualified deputies, but the CI always retains overall responsibility.]

### 5.5.3 CCO:

- Central data collection and verification of SAEs according to the trial protocol.
- Reporting safety information to the CI for the ongoing assessment of the trial's risk / benefit.
- Reporting safety information to the independent oversight committees identified for the trial (DMC and/or TSC) according to the Trial Monitoring Plan.
- Expedited reporting of SUSARs to the Competent Authority (MHRA in UK), and Sponsor and REC within required timelines.
- Notifying local PIs of any SUSARs that occur within the trial.
- Checking for and notifying local PIs of updates to the Reference Safety Information for the trial.
- Preparing standard tables and other relevant information for the DSUR in collaboration with the CI and ensuring timely submission to the MHRA and REC.

### 5.5.4 Trial Steering Committee:

The TSC will review safety data and liaise with the DMC regarding safety issues on a regular basis, with frequent meetings during recruitment, and with the option of unplanned meetings if required.

### 5.5.5 Data Monitoring Committee:

The DMC will annually review unblinded overall safety data to determine patterns and trends of events, or to identify safety issues, which would not be apparent on an individual case basis, with the option of more frequent meetings. There will also be a chairperson's review every 6 months.

## 6 STATISTICS AND DATA ANALYSIS

### 6.1 SAMPLE SIZE CALCULATION

Availability of prospective NHS Scotland DES data allowed progression rates for DR to be calculated directly from the target population in which LENS will be conducted. Data in Table 6 indicate DR progression rates (limited to patients with at least 3 years' follow-up and a baseline result prior to 2009). If it is assumed that participants will be recruited from among the various grades with observable DR in proportion to their prevalence, the progression rate from observable to 'referable' DR would be approximately 29% over 4 years. On that basis, 1060 participants would yield approximately 222 events over an average follow-up of 4 years, providing 85% power to detect a 33% reduction in progression (allowing for 15% drop-out) at alpha = 0.05. We aim to randomise at least 1060 participants.

As described in LENS' inclusion criteria, patients with R1 DR will need to have bilateral rather than unilateral R1 given that progression rates to referable DR are 2.4X and 3.7X higher in type 1 DM and type 2 DM respectively with bilateral R1 compared with unilateral R1. Inclusion of patients with unilateral R1 would substantially reduce event rates.

The LENS composite primary outcome consists of progression of observable DR to referable DR, or any of retinal laser therapy, vitrectomy or intra-vitreal injection of medication due to DR. While DR progression is likely to dominate in terms of numbers of events, this composite outcome has been selected to avoid missing any unexpected rapid progression of DR which requires intervention before the next DES screening visit.

**Table 6.** Progression rates of DR in Scotland (baseline data pre-2009)

	Progression to referable retinopathy or maculopathy over 3 years*			
Baseline grading	M2	R3	R4	M2 or R3 or R4
Type 1 DM (n=14,354)				
R0 M0 (n=7,202)	131 (1.8%)	204 (2.8%)	12 (0.2%)	347 (4.8%)
R1 (one eye) M0 (n=2,480)	170 (6.9%)	21 (0.9%)	24 (1.0%)	215 (8.7%)
R1 (both eyes) M0** (n=4,016)	622 (15.5%)	121 (3.0%)	102 (2.5%)	845 (21.0%)
R2 or M1** (n=656)	237 (36.1%)	64 (9.8%)	48 (7.3%)	349 (53.2%)
Type 2 DM (126,639)				
R0 M0 (n=92,543)	942 (1.0%)	73 (0.1%)	82 (0.1%)	1,097 (1.2%)
R1 (one eye) M0 (n=20,147)	822 (4.1%)	62 (0.3%)	45 (0.2%)	929 (4.6%)
R1 (both eyes) M0** (n=11,978)	1,663 (13.9%)	264 (2.2%)	128 (1.1%)	2,055 (17.2%)
R2 or M1** (n=1,971)	530 (26.9%)	184 (9.3%)	60 (3.0%)	774 (39.3%)

\*data available for those screened prior to 2009 and with at least 3 years of follow-up; therefore, these numbers do not accurately reflect numbers available for recruitment (45% greater at last count)

\*\*patient groups to be recruited in LENS; proportional recruitment from each of these groups provides 29% progression over 4 years

### 6.1.1 Planned recruitment rate

It is estimated that there are >20,000 patients in Scotland meeting the DR eligibility criteria for LENS. It will be necessary to recruit approximately 5% of these individuals. Due to the opportunity to perform preliminary screening before meeting potential participants, it is anticipated that face to face screening will be highly efficient. The use of an active run-in phase is designed to include individuals who are likely to remain adherent to trial procedures, thereby maximising the trial's ability to detect a true effect of the study treatment. We anticipate 25% loss of patients during the screening and active run-in phases combined. Approximate total recruitment targets for randomised participants in each health board site are listed below, and these are determined by population.

NHS Greater Glasgow and Clyde	245
NHS Forth Valley	62
NHS Lothian	170
NHS Grampian	115
NHS Lanarkshire	114
NHS Tayside	84
NHS Fife	75
NHS Ayrshire and Arran	75
NHS Highland	64
NHS Dumfries and Galloway	32
NHS Borders	24
TOTAL	1060

Using the opening of the first site for screening visits as Month 0, we aim to recruit approximately the following numbers: 69 participants at 6 months, 368 at 12 months, 729 at 18 months and 1060 at 24 months from the start of recruitment. These estimates are based on opening all sites over a seven month period and aiming to open sites in the largest health boards first, with modest recruitment for the first two months followed by stable recruitment until the end of the recruitment period.

## 6.2 STATISTICAL ANALYSIS

The trial data will be held in a secure database in the CCO with controlled access in line with departmental security policies. Analyses will be performed in accordance with a pre-specified Statistical Analysis Plan (SAP), which will be written by the trial statisticians and approved by the TSC prior to any unblinding of study results, and which will describe in detail the methods used to analyse each outcome and the approaches used to handle any missing data. All analyses will be done according to the “intention-to-treat” principle (i.e. participants will be analysed in the group to which they were randomised, no matter what treatment they received, and regardless of whether they deviated from the protocol in any way). The primary analysis of the primary outcome will be considered statistically significant at the 5% significance level. For secondary and, particularly, tertiary outcomes, and also for secondary analyses of the primary outcome, allowance in their interpretation will be made for multiple hypothesis testing, taking into account the nature of events (including timing, duration and severity) and evidence from other studies. In addition to the pre-specified comparisons, other analyses may be performed with due allowance for their exploratory and, perhaps, data-dependent nature.

### 6.2.1 Interim analysis and criteria for the premature termination of the trial

Unblinded interim analyses will be reviewed annually by the DMC, and will be conducted and presented by a statistician not involved in the day-to-day management of the trial. Upon review of such data, the DMC will advise the Steering Committee if, in their view, the randomised comparisons have provided both (a) proof beyond reasonable doubt that for all patients, or for some specific types, fenofibrate therapy is clearly indicated or contra-indicated; and (b) evidence that might reasonably be expected to influence materially the patient management of many clinicians. The TSC can then decide whether to end or modify the trial or to seek additional data, and this decision will be communicated in writing to the CI after each TSC meeting. Only members of the DMC will have access to unblinded results during the conduct of the trial. Any decision by the DMC which is deemed relevant to the safety of participants will be reported in an expedited fashion to the MHRA.

Appropriate criteria of proof beyond reasonable doubt cannot be specified precisely, but the DMC will work on the principle that a difference of at least 3 standard errors in an interim analysis of a major outcome event may be needed to justify halting, or modifying, a study before the planned completed recruitment. This criterion has the practical advantage that the exact number of interim analyses would be of little importance, and so no fixed schedule is proposed.

### 6.2.2 Economic evaluation

An economic evaluation will be carried out alongside the trial, adopting a health service perspective on costs and a patient perspective on health benefits. The cost of providing the study drug over and above standard care will be estimated based on drug prescription and administration costs. Any increase in primary care monitoring (e.g. blood and urine testing) will be captured from the SCI Diabetes system. All secondary care health service resource use will be captured by electronic linkage to routine datasets: SMR01 for all inpatient and day case activity; SMR00 for all outpatient contacts (<http://www.ndc.scot.nhs.uk/National-Datasets/index.asp>). DR specific referrals and procedures will be captured using a combination of cross checked sources: the SCI diabetes system; relevant OPCS codes from SMR01 (SMR00 for ophthalmology outpatient referral and monitoring visits); and the trial specific questionnaire (with verification of reported events by a research nurse cross checking against NHS records). All resource use events will be valued using appropriate national unit prices. The study drug will be costed at list price (by dose and quantity) as reported in most up to date version of the BNF (2015). DR related procedures will be costed where possible using the Scottish national tariff for the relevant health care resource grouping (<http://www.isdscotland.org/Health-Topics/Finance/Scottish-National-Tariff/>), whilst other inpatient and outpatient care will be costed using Scottish specialty unit cost data (ISD 2015). Primary care contacts will be costed using Personal Social Services Research Unit cost data (2015), and resultant biochemistry tests will costed based on ISD reported unit costs for relevant laboratory services (ISD 2015). Following compilation of the cost dataset, the total health service cost will be estimated for each participant from baseline through to 4 years post randomisation.

Analysis of the economic data will be performed by intention to treat in accordance with a pre-specified economic analysis plan (to be completed before unblinding of the data). The mean difference in total service costs between treatment allocation groups will be estimated using generalised linear regression adjusted for minimisation and baseline covariates (e.g. baseline health status) as appropriate. Costs will be assessed against the primary outcome, and the incremental cost per progression of DR (or DR related intervention) averted will be estimated for fenofibrate versus placebo. In addition, participant responses to the EQ-5D, at baseline and follow-up, will be used to estimate QALYs for each participant. The mean difference in QALYs between the groups will be estimated using generalised linear regression, allowing the incremental cost-per QALY to be estimated for fenofibrate versus placebo based on data collected to 4 years.

If the use of fenofibrate is found to result in an increased cost to the health service at four years, for a modest reduction in progression and a QALY gain of insufficient size to justify the extra cost, modelling will be used to extrapolate costs and QALYs beyond the follow-up period of the trial. This will rely on the fitting of parametric survival curves to the observed progression data, to predict progression beyond four years. Further downstream treatment/monitoring costs (associated with progression), and visual acuity and quality of life outcomes of referable disease, will then be modelled using a combination of data collected within the trial and published data on expected outcomes of treatment. This will allow longer-term cost-effectiveness, in terms of the incremental cost per QALY gained, to be estimated for fenofibrate versus placebo. The robustness of any

model based estimates of cost-effectiveness will be assessed using deterministic and probabilistic sensitivity analysis.

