**TRIAL SUMMARY**

Trial Title	A phase 4 randomised placebo-controlled clinical trial of fenofibrate to prevent progression of non-proliferative retinopathy in diabetes
Internal ref. no. (or short title)	LENS: Lowering Events in Non-proliferative retinopathy in Scotland
Clinical Phase	4
Trial Design	Randomised double-blind placebo-controlled trial
Trial Participants	Adult participants with diabetes and observable retinopathy
Planned Sample Size	At least 1,060 participants (approximately 530 on fenofibrate tablets and 530 on placebo tablets)
Follow-up duration	At least 4-years after randomization of the median patient and at least 222 primary outcome events
Planned Trial Period	6 years
Primary research objective	To estimate the effect of allocation to fenofibrate versus placebo on progression to the composite primary outcome of referable diabetic retinopathy (DR) or any of the following treatments for DR: retinal laser therapy, vitrectomy or intra-vitreal injection
Secondary research objectives	
To estimate the effect of allocation to fenofibrate versus placebo on:
 
 
• The composite primary outcome in various subgroups
 
• Individual components of the composite primary outcome
 
• Any progression of DR across the Scottish Diabetic Eye Screening (DES) grading scale
 
• Visual acuity
 
• Hard exudates or blot haemorrhages by the macula
 
• Macular oedema
 
• Visual function and quality of life
 
 
To evaluate the:
 
 
• Total cost to the health service (in terms of additional drug treatment and monitoring costs, and health care resource use over follow-up)
 
• Cost-effectiveness (in terms of incremental cost per QALY gained with fenofibrate versus placebo)
 

Investigational Medicinal Product	Fenofibrate
Formulation, Dose, Route of Administration	One 145mg nanoparticle fenofibrate tablet or matching placebo tablet daily (or one tablet every second day in the context of chronic kidney disease) taken orally

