LENS will recruit and randomise at least 1,060 patients with diabetes and retinopathy to receive either fenofibrate or placebo tablets, to be taken orally, for at least a median of 4 years (counted as 4 years from randomization of the median participant). Prior to randomisation, all participants who are eligible at screening will enter an active run-in phase in which they will be treated with open-label fenofibrate tablets for approximately 8 weeks. The purposes of the active run-in are to:

- i) maximise adherence during the trial, thereby providing robust results, and
- ii) allow the research team to establish the best dosing regimen for each participant during the trial.

The dose of fenofibrate tablets to be used in LENS is 145mg. Each participant's dosing regimen will be determined by their renal function. Those with normal renal function will take one fenofibrate tablet daily during the active run-in and one study tablet (fenofibrate or placebo) daily after randomisation, whereas participants with chronic kidney disease will take one fenofibrate every second day during the active run-in and one study tablet every second day after randomisation.

**Table 1.** Scottish DES Collaborative grading system for DR

Grading	Description	Outcome
RETINOPATHY (excluding the macula)		
R0	No DR anywhere	Rescreen in 12-24 months
R1*	
Background DR – mild
 
The presence of at least one of any of the following features anywhere
 
 
• dot haemorrhages
 
• microaneurysms
 
• hard exudates
 
• cotton wool spots
 
• blot haemorrhages§
 
• superficial/ flame shaped haemorrhages
 
	Rescreen in 12 months
R2*	
Background DR – observable
 
Four or more blot haemorrhages§ in one hemi-field only (Inferior and superior hemi-fields delineated by a line passing through the centre of the fovea and optic disc)
	Rescreen in 6 months
R3	
Background DR – referable
 
Any of the following features:
 
 
• Four or more blot haemorrhages§ in both inferior and superior hemi-fields
 
• Venous beading
 
• IRMA
 
	Refer to ophthalmology
R4	
Proliferative DR
 
Any of the following features:
 
 
• Active new vessels
 
• Vitreous haemorrhage
 
	Refer to ophthalmology

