## 4.10 END OF TRIAL

The trial will continue until at least 222 primary events have occurred and until median follow-up is at least 4 years, whichever is the later. The 'end of study' is defined as the date on which the trial database is locked for the primary analysis. The Trial Steering Committee (TSC) has the right to terminate the study for clinical or administrative reasons at any time.

The end of the study will be reported to the REC and Regulatory Authority within 90 days, or 15 days if the study is terminated prematurely. Investigators will notify participants and inform them of appropriate procedures to follow. A summary report of the study will be provided to the REC and Regulatory Authority within one year of the end of the study.

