## 12.3 APPENDIX 3 – SCHEDULE OF ASSESSMENTS

PROCEDURE	Screening Visit	Randomisation visit	Subsequent telephone / email follow-up (every 6 months for at least 3 years unless stated otherwise)
Informed consent	X		
Inclusion / exclusion criteria	X	X	
Record demographics	X	X	
Medical History	X	X	
Lifestyle factors	X		
Concomitant medications	X	X	
Height		X	
Weight		X	
Vital signs		X	
Blood eligibility biochemistry	X a	X a	
Blood HbA1c	X		
Blood lipids (random)	X		
Urine albumin creatinine ratio	X		
Trial-specific Questionnaire (by telephone or medical records)			X
EQ-5D questionnaire (on paper)	X		X d
VFQ-25 questionnaire (on paper)	X		X d
Open-label fenofibrate mail-out (10 week supply)	X b		
Blinded drug mail-out (26 week supply)		X	X
Compliance with study treatment		X	X
Randomisation		X c	
Willingness to start and/or continue study treatment	X	X	X

a U&E, LFTs (including at least one of ALT and AST), CK

b run-in drug mail-out will not be immediate as it will first be necessary to verify biochemistry; the initial mail-out of open-label fenofibrate will be followed by a phone call 2-3 weeks later to verify receipt by the participant

c randomisation will not occur at the time of the visit as it depends on visit biochemistry; starting dose frequency will depend on renal function

d for completion after 24 months and then at the final assessment

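### Does the 4-year cost and QALY horizon fail because the stopping rule guarantees 4 years only to the median participant?

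*Protocol*

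**What the plan says.** Protocol 6.2.2 sets the cost horizon: "the total health service cost will be estimated for each participant from baseline through to 4 years post randomisation". For health benefit it says "The mean difference in QALYs between the groups will be estimated using generalised linear regression", with cost per QALY based on the data to 4 years. It names minimisation and baseline covariates for the cost regression and none for the QALY regression. It also says the economic analysis will follow its own pre-specified plan, finished before the data are unblinded. SAP 4.4.3 defers to a separate document in the same way.

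Protocol 4.10 continues the trial to at least 222 primary events and "until median follow-up is at least 4 years, whichever is the later". Protocol 2 explains the median as "counted as 4 years from randomization of the median participant", and the Trial Summary agrees: "At least 4-years after randomization of the median patient". The Trial Summary also gives a planned trial period of 6 years without saying when it starts.

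The Schedule of Assessments (Appendix 3) describes contact "every 6 months for at least 3 years unless stated otherwise". Its footnote for EQ-5D after screening reads "for completion after 24 months and then at the final assessment".

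**The concern.** A 4-year total for every participant and a stopping rule tied to the median do not fit together exactly. Anyone randomised after the median participant may be followed for less than 4 years. Follow-up after the main study needs a further protocol (4.6.5), so it cannot be counted on to complete their records.

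The analyst must then drop these participants, treat truncated totals as complete, or adjust for the unobserved time. SAP 7.4 covers event dates, missing subgroup values and repeated continuous measures. SAP 7.5 covers censoring of time-to-event endpoints. Neither covers costs or QALYs. The modelling in 6.2.2 is conditional and looks beyond the trial, so it does not fill gaps inside the 4-year window.

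EQ-5D adds to the worry. With one measurement at 2 years and one at the end, most participants have no utility value exactly at 4 years. If truncated totals were analysed as complete, 4-year incremental costs and QALYs would both be understated. A method chosen after unblinding could also be chosen to suit the result.

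**Working it through.** **Inputs.** Sample size 1,060, 222 events, 33% reduction, 85% power, 29% progression over 4 years and 15% drop-out are from Protocol 6.1. The two-sided 0.05 level is from SAP 7.2. Cumulative accrual of 69, 368, 729 and 1,060 at months 6, 12, 18 and 24 is from Protocol 6.1.1 ("729 at 18 months and 1060 at 24 months from the start of recruitment"). The stopping rule is from Protocol 4.10. Accrual is taken as linear between the stated points. Death and withdrawal are left out.

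**The plan's own event figure.** Schoenfeld's formula gives 4 × (1.960 + 1.036)² / (ln 0.67)² = 224. The expected yield is 530 × [0.29 + (1 − 0.71^0.67)] × 0.85 = 530 × 0.495 × 0.85 = 223. The stated 222 is reproduced. With constant hazards and 15% drop-out, about 244 events are expected by month 62.7, so the event criterion is not expected to prolong the trial. The median criterion sets the earliest end.

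**Earliest permitted end.** The 530th randomisation falls at month 12 + 6 × (530 − 368)/(729 − 368) = 14.7. The earliest stop is 14.7 + 48 = month 62.7. Follow-up then runs from 3.2 to 5.2 years.

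**Shortfall at that date.**

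- 729 − 530 = 199 people enter between months 14.69 and 18. Their mean shortfall is 3.31/2 = 1.65 months, or 329 person-months in all.
- 1,060 − 729 = 331 people enter between months 18 and 24. Their mean shortfall is 3.31 + 3 = 6.31 months, or 2,088 person-months in all.
- The total is 2,417 person-months = 201.4 person-years. The full window holds 1,060 × 4 = 4,240 person-years, so 4.75% is unobserved.
- The average over the 530 affected is 2,417/530 = 4.6 months, and the maximum is 9.3.

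**Later end dates.**

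| Stop | Share under 4 years | 4-year person-time unobserved |
|---|---|---|
| Month 62.7 | 50% | 4.75% |
| 3 months later | 33% | 2.2% |
| 6 months later | 17% | 0.6% |
| 9 months later | 1.6% | 0.01% |
| Month 72 | 0% | 0% |

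Month 72 is where the 6-year planned period ends if it is counted from the first site opening, which is an assumption. If accrual were instead uniform over 12 to 36 months, the unobserved share at the earliest end would be 3.1% to 9.4%.

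**Worst-case effect on the ratio.** Suppose truncated totals were analysed as complete at the earliest end, and let f be each participant's observed share of 4 years.

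- If costs and QALY gains accrue evenly, both scale with mean f = 0.9525 and cost per QALY is unchanged.
- If the utility gain grows linearly with time (an assumption), QALY gains scale with mean f² = 0.9111, a loss of 8.9%. Cost per QALY is then too high by 0.9525/0.9111 = 1.045, or about 4.5%. That error works against fenofibrate.

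**EQ-5D timing.** If all final assessments fall on the stop date, then at month 62.7 17% are more than 6 months before 4 years, 19% more than 6 months after, and 64% within 6 months. At month 72 none are early and 729/1,060 = 69% are more than 6 months after. A late final value leaves 4 years bracketed by two measurements, so interpolation is enough. Extrapolation is needed only for those whose final assessment is early.

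**The case for a change.** The strongest case for a change is that total cost and cost-effectiveness are pre-specified secondary outcomes (Protocol 3.2.2), and Protocol 6.2 says the SAP will set out how missing data are handled for each outcome. The SAP passes this on instead. Section 6.2.2 already fixes the horizon, the regression family and the cost covariates, so a sentence on incomplete follow-up would sit naturally beside them and would cost little. The 6-year period is a plan, not a guarantee. Even if it is met, EQ-5D still needs an interpolation rule.

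The factual part stands: the two documents contain no such rule, and the stopping rule does allow records shorter than 4 years. The harm does not follow. It needs truncated totals to be treated as complete, and 6.2.2 neither says nor implies that. The demand that the method be fixed before unblinding is already a commitment in 6.2.2. Interpolating utilities between visits is ordinary area-under-the-curve practice.

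The silence on QALY covariates does not show that adjustment is left out. Section 6.2.2 already draws on baseline EQ-5D for the QALY calculation and provides for covariate adjustment in the cost model.

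The cost gap may also be smaller than the table shows. Costs come largely from routine linkage, 4.10 ends the study at database lock, and 5.3.1 collects adverse-event data until the final registry linkages. If cost linkage also ran on past the last contact, which is not stated, part of the missing time would be recovered.

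**Conclusion.** No change to the protocol or SAP follows. The mismatch between a fixed 4-year horizon and a median-based stop is real but small. At most about 4.8% of the 4-year person-time is unobserved under planned accrual, and none if the trial ends at month 72. The shortfall comes from the calendar, so it is balanced between arms and attenuates totals; it does not favour either treatment. It has no bearing on the primary analysis, where Cox regression handles the censoring.

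What is missing is method detail that both documents assign to the economic analysis plan. A competent author of that plan would address incomplete follow-up, interpolation of EQ-5D to 4 years and baseline adjustment of QALYs as a matter of course. A colleague who holds the plan can confirm those three points in a few minutes.

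The sizes rest on the planned accrual with linear interpolation, a single calendar stop date, and no allowance for death or withdrawal. Slower recruitment would raise the figure, to 9.4% for uniform accrual over 36 months. The conclusion also rests on the economic plan being completed before unblinding, as 6.2.2 requires. Its contents could not be checked here.
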